4.1.1 International Board-Certified Lactation Consultation (IBCLC)

An International Board-Certified Lactation Consultant (IBCLC) is a healthcare professional who specialises in the clinical management of breastfeeding. IBCLCs are certified by the International Board of Lactation Consultant Examiners (IBLCE), an international organisation that sets standards for lactation consulting.

IBCLC intervention includes education, guidance, and support to help mothers overcome breastfeeding challenges such as latch issues, low milk supply, and other breastfeeding-related concerns. IBCLCs work in hospitals, clinics, private practices, and community settings.

Consultations with the IBCLC will include:

- Breastfeeding assessment
- Education
- Latch and positioning techniques
- Advice on pumping and expressing milk
- Breastfeeding and nutritional counselling
- Growth and development monitoring
- Emotional support, counselling and problem solving
- Measurement of weight, length, and head circumference to track growth
- Assessment of vital signs, including heart rate, respiratory rate, and temperature

4.1.2 Osteopathic Manual Therapy

Osteopathy is a form of manual medicine that focuses on the musculoskeletal system and its impact on overall health. Osteopaths use a hands-on approach to diagnose and treat a range of health issues. An OMT treatment only includes gentle manual techniques such as massage, cranial osteopathy, and/or myofascial release to areas of tension in the infant's body.

Consultations with the Osteopath will include:

- Medical history taking, including pregnancy, birth and infant medical history
- Postural education for both mother and baby during feeding, breastfeeding assessment, latch and suck function [20, 30-33]
- Positioning assessment [18, 34, 35]
- Musculoskeletal and health screen of infants including assessment of musculoskeletal trauma or birth trauma, plagiocephaly [36-38] or torticollis [17, 39, 40])
- Monitoring of developmental milestones [41, 42] and cognitive development. [43]
- Sleep habit and sleep safety assessment[38]
- Head preference and infant positioning assessment,
- Crying habit assessment [23, 38]

Osteopathic Paediatric Physical Examination: Includes the following [41,42)

- Examination of the skin, eyes, ears, nose, tongue, palate and throat
- Inspection of the abdomen for any abnormalities or signs of discomfort

- Evaluation of muscle tone and primitive reflexes and established reflexes
- Examination of the spine, pelvis, hips and peripheral joints [38]
- Examination of facial, jaw and cranial asymmetry [17, 44, 45]
- Examination of infant suck function

Gentle Osteopathic Techniques for infant musculoskeletal care may include

Cranial Osteopathy

Paediatric osteopaths may use gentle manual techniques to assess and address any restrictions or imbalances in the infant's musculoskeletal system, including the cranium, face, jaw, cervical spine and associated musculoskeletal structures. The idea is that releasing tension in these areas may help the infant feel more comfortable and relaxed, which then may positively influence breastfeeding and alleviate issues such as difficulty latching, maintaining latch and maternal pain [18, 19, 46].

Oral assessment and suck function:

Paediatric osteopaths may assess the oral anatomy, structure and function, palate shape, buccal and oral muscular tone, as well as infant suck function. This often includes assessment of tethered oral tissues that may be inhibiting infant suck function. Treatment may involve gentle techniques to release tension in the affected area as well as referral to a general practitioner or paediatrician for ankyloglossia assessment and medically guided management [47-49].

Myofascial Release: Paediatric osteopaths may use myofascial release techniques to address tension in the muscles and connective tissues around the baby's mouth, face, and neck. This can be especially relevant for babies experiencing difficulty latching or sucking effectively [50, 51].

4.1.3 Identification and selection of osteopathic and IBCLC practitioners

Practitioners will be selected based on the level of their clinical experience and training. All participating osteopaths and IBCLCs must have post-graduate training (in paediatrics for osteopaths and current board certification in lactation consulting for IBCLCs), be currently registered/certified with their governing bodies, have appropriate insurance, have a minimum 10 years of experience in managing infant breastfeeding and paediatrics and have a valid working with children/vulnerable population check.

All participating practitioners will undergo pre-trial procedures training. A section on research ethics, confidentiality, privacy, and sharing/handling of information will form part of the pre-trial training of participating IBCLCs and osteopaths.

All participating practitioners must also complete *the Global Health Training Centre - Good Clinical Practice Course*: <https://globalhealthtrainingcentre.tghn.org/ich-good-clinical-practice/>

An invitation will be emailed to the IBCLC and osteopathic professions calling for expressions of interest, The information for practitioners and poster will be added as attachments to this email (see Appendices 4.1 and 5.1).

All professionals will then be contacted via a phone call and be selected by the CI and co-investigators.

4.1.4 Trial design

All participants will require a pre-screen appointment to assess their eligibility to join the trial.

All participants will receive a maximum of two IBCLC face-to-face sessions and two IBCLC telehealth calls over a 4-week period. In addition to this, the IBCLC group will receive up to two additional telehealth consultations if required whereas the IBCLC + OMT group will receive up to three OMT consultations.

Outcome measures will be administered at baseline and again at weeks 4 and 8. At 8 weeks, all participants will receive a follow-up phone call/email from the trial coordinator, which will gather information on the breastfeeding status of the MID.

[figure not shown]

Figure 1: Flow chart

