PROTOCOL DOCUMENT FOR THE BREASTFEEDING OSTEOPATHIC MANUAL THERAPY STUDY (BROMS)

[name]
[name]
Adjunct Associate [name]
Associate [name]

Protocol for the Breastfeeding Osteopathic Manual Therapy Study

This Project Description provides the scientific and academic background and context for the research project 'Breastfeeding Osteopathic Manual Therapy Study (*BROMS*)'.

Summary:

This study is a two-armed, multi-centre, pragmatic, randomised clinical trial designed to examine the effect of osteopathic care (OMT) on breastfeeding dyads experiencing breastfeeding difficulty. The trial will be conducted in two stages: preliminary and full. Both stages have the same design.

The preliminary stage will pilot the design at a single clinic in Melbourne by recruiting 16 mother-infant dyads (MIDs) experiencing breastfeeding difficulty. The full stage will extend the pilot to multiple clinics across Melbourne and Canberra (See Appendix 1.1 – Clinic Consent Form).

Participants in both stages will be randomly allocated to one of two groups: international board-certified lactation consultant (IBCLC) - Standard care (Control) or IBCLC plus osteopathic intervention (OMT) (Experimental). The full stage will continue the pilot stage and see a further 54 MIDs (total N=70) experiencing breastfeeding difficulty randomly allocated to the same two groups. Recruitment for this stage will be from osteopathic clinics, maternal health centres and breastfeeding drop-in centres across metropolitan Melbourne and Canberra.

Each participant will undergo 4 weeks of intervention with a follow-up phone call one-month post-intervention.

The primary outcome of the study is change in infant breastfeeding function as measured by the Bristol Breastfeeding Assessment Tool (BBAT).

Secondary outcomes include maternal breastfeeding confidence, as measured by the Breastfeeding Self-efficacy Scale – Short form (BSES-SF) and changes in breastfeeding symptoms such as maternal breastfeeding-related pain, infant ability to latch and maintain latch to the breast and feeding noise at the breast measured using a series of visual analogue scales (VAS).

1. Study details

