1.7 Gaps in the research

- The effectiveness of OMT for infants with breastfeeding issues remains unclear
- Identification of the possible anatomical musculoskeletal structures involved in breastfeeding dysfunction is yet to be determined.
- The benefits of combining IBCLC with osteopathic care are unknown.

2. Aim of Research

The aim of this project is to investigate the efficacy of OMT intervention designed to address musculoskeletal dysfunction in the infant with breastfeeding difficulty.

2.1 Research questions:

This research aims to answer the following research questions:

1. Does OMT intervention deliver additional improvements in breastfeeding compared to standard care (IBCLC) in infants with breastfeeding difficulty?
2. Does OMT intervention deliver additional improvements in breastfeeding mechanical function compared to standard care (IBCLC) in infants with breastfeeding difficulty?
3. Does OMT intervention deliver additional improvements in maternal breastfeeding confidence compared to standard care (IBCLC) in infants with breastfeeding difficulty?

2.2 Research Hypotheses:

This study aims to test the following research hypotheses:

1. OMT intervention to the infant improves breastfeeding more than standard care (IBCLC) in infants with breastfeeding difficulty.
2. OMT intervention to the infant improves breastfeeding mechanical function more than standard care (IBCLC) in infants with breastfeeding difficulty.

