12.0 Recruitment Duration and Study Duration

It is anticipated that the recruitment phase of the trial will be 12 months. If the target recruitment number is not reached in that time, there is provision to extend the recruitment period by a further 6

months. The entire project will run over a 2-year period (Figure 2). Each participant will be involved for a total of 8 weeks.

13.0 Participant time commitment:

The total time commitment for each participant is 330 or 360 minutes (6-6.5 hours) (See Table 1). We acknowledge that in some circumstances, there will be an inequality of 10% in the total time spent for each group. We believe this is acceptable given the nature of the trial.

	INTERVENTION	IBCLC (Minutes)	IBCLC/OMT (Minutes)
Week 0	Baseline Measurements (Face-to Face)/Paperwork (Online)	60	60
Week 1	IBCLC 1	60	60
Week 2	IBCLC 2	30	30
	OMT 1		60
Week 3	Up to 2 x 1/2-hour IBCLC Telehealth	60	
	Up to 2 x ¼ - hour IBCLC telehealth		30
	OMT 2		30
Week 4	Up to 2 x 1/2 - hour IBCLC Telehealth (as required)	60	
	OMT 3 (as required)		30
	Post Intervention paperwork (Online)	30	30
Week 8	Discharge paperwork - Follow up Phone call	30	30
	Total Minutes	330	360

Table 1: Participation for each group

- IBCLC 1 Initial Consultation with an IBCLC
- IBCLC 2 Follow-up Consultation with IBCLC
- OMT 1 Initial Consultation with an Osteopath
- OMT 2 & 3 Follow-up Consultation with Osteopath

Practitioners must also complete a 4-hour pre-trial training and a 1-hour Global Health Training Centre—Good Clinical Practice Course.

Participants will be followed up 1 month after finishing the intervention phase of the trial. At that follow-up they will be asked to complete the BSES-SF and VAS measures via email and participate in a short 5-minute telephone conversation with the trial coordinator about their current breastfeeding status.

If they are continuing to have difficulty breastfeeding and need further support, they will be referred to the Australian Breastfeeding Association where breastfeeding support counsellors are available free of charge.

15 Data Collection

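### The IBCLC + OMT arm is not the control's lactation care plus osteopathy (IBCLC ceiling 120 vs 210 min), so section 2 should state a comparison of two care packages

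*Protocol*

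**What the plan says.** The Summary names the experimental arm "IBCLC plus osteopathic intervention (OMT) (Experimental", against IBCLC as standard care. Section 2 sets out to "investigate the efficacy of OMT intervention designed to address musculoskeletal dysfunction in the infant". The three research questions in section 2.1 ask whether OMT brings improvement additional to IBCLC standard care, and the hypotheses in section 2.2 are that it improves outcomes more than that care.

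Section 4.1.4 sets the contacts. For everyone: "All participants will receive a maximum of two IBCLC face-to-face sessions and two IBCLC telehealth calls over a 4-week period". It then says that "the IBCLC group will receive up to two additional telehealth consultations if required", while the other arm may have up to three osteopathic consultations.

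Section 4.1.4 counts contacts but gives no lengths. Those are in Table 1 of section 13.0. For the week-3 calls, control has "Up to 2 x 1/2-hour IBCLC Telehealth" and the OMT arm has "Up to 2 x ¼ - hour IBCLC telehealth". In week 4, control alone has "Up to 2 x 1/2 - hour IBCLC Telehealth (as required". The text above Table 1 accepts a difference of about 10% between the arms in total participant time. It does not mention the difference in IBCLC time.

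**The concern.** A label of the form A versus A plus B, with questions about what B adds, tells the reader that A is the same in both arms. Here it is not. The OMT arm is offered less lactation-consultant time than control, partly through a difference in call length that section 4.1.4 does not show. A reader of sections 2 and 4.1.4 alone would take the common base as identical.

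What is at stake is the conclusion. Under the present wording a null result would be read as OMT adding nothing to IBCLC care, although the OMT arm may have had less of that care. A positive result would be read as the effect of manual therapy, although the arms also differ in IBCLC time and in who gives feeding advice. The schedule supports neither statement.

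**Working it through.** **Inputs.** All minutes come from Table 1 (section 13.0) and are maxima.

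| Item | Control | OMT arm |
|---|---|---|
| IBCLC 1, week 1 | 60 | 60 |
| IBCLC 2, week 2 | 30 | 30 |
| Common telehealth, week 3 | 2 × 30 = 60 | 2 × 15 = 30 |
| As-required telehealth, week 4 | 2 × 30 = 60 | 0 |
| **IBCLC ceiling** | **210** | **120** |
| OMT 1, 2 and 3 | 0 | 60 + 30 + 30 = 120 |
| Baseline, post-intervention, week 8 | 60 + 30 + 30 = 120 | 60 + 30 + 30 = 120 |
| **Total** | **330** | **360** |

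**Plan's own figures.** The totals of 330 and 360 min match Table 1, so the table has been read correctly. The difference in total time is 30/330 = 9.1%, consistent with the stated 10%.

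**IBCLC gap at the ceiling.** 210 − 120 = 90 min, and 90/210 = 43% less in the OMT arm.

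**Source of the gap.** Face-to-face IBCLC time is equal (60 + 30 = 90 min in each arm), so the whole gap is telehealth: 120 vs 30 min.
- Call length, week 3: 60 − 30 = 30 min, one third of the gap.
- As-required calls, week 4: 60 − 0 = 60 min, two thirds of the gap.

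**Range.** Assume that both arms take up the common calls equally.
- No telehealth used: 90 vs 90, gap 0.
- Both common calls, no as-required calls: 150 vs 120, gap 30 min (30/150 = 20%).
- Everything used: 210 vs 120, gap 90 min.

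**Timing.** Only the week-3 difference, at most 30 min, falls before week 4, the week of the post-intervention measures.

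**Total practitioner contact.** Control 210 min; OMT arm 120 + 120 = 240 min. The plan roughly balances contact minutes. A literal add-on arm would offer 210 + 120 = 330 min.

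**Overlap of content.** Section 4.1.2 includes in the osteopath's consultation postural education for feeding and assessment of breastfeeding, latch, suck and positioning. Section 4.1.1 lists breastfeeding assessment and help with latch and positioning under IBCLC care. The osteopathic visits may therefore replace some of the IBCLC time not offered. Section 3.2 places OMT at the clinics. If all OMT visits are in person, face-to-face time is at most 90 min in control and 90 + 120 = 210 min in the OMT arm. The arms then differ in mode of contact as well as in content.

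**The case against.** The strongest reply is that nothing here is false. Section 2 compares OMT with IBCLC standard care, the Summary defines standard care as the control arm, and the trial calls itself pragmatic. On that reading the hypotheses already compare two packages as delivered. Section 4.1.4 openly describes the extra control calls, and Table 1 prints every contact and its length by arm. Section 4.1.4 gives the number of common calls but not their length, so Table 1 adds to it and does not contradict it. The 90 min is an extreme, and most of it is as-required time in the week of the post-intervention measures.

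Much of this stands. The extra calls are disclosed, the gap may be small or nil in practice, and a package reading of the hypotheses is possible. What remains is that the arm label, the aim of showing OMT's efficacy and the wording about additional improvement all point to an add-on effect. The halved length of the common calls is not explained, and the accepted 10% concerns total time, where the OMT arm has more.

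A reader might infer three stronger things, none of which the protocol supports:
- **That the design is invalid.** Exchanging IBCLC calls for osteopathic visits at similar total contact is a legitimate choice.
- **That the gap biases the trial against OMT, so a positive result is safe.** Less IBCLC time alone would point that way if such time helps. However, osteopathic visits carry overlapping feeding support and probably more in-person contact, so the net direction is unknown.
- **That failing to plan for recording delivered minutes is a fault.** The list in section 4.6 does not claim to be complete, and such recording is commonly settled elsewhere.

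**Conclusion.** The point holds as a minor fault of wording with a real effect on what may be concluded. The schedule compares a shared IBCLC base plus osteopathic consultations with that base plus more IBCLC telehealth, whereas section 2 states the add-on efficacy of OMT. The IBCLC ceilings are 210 and 120 min. If uptake of the common calls is equal, the delivered gap lies between 0 and 90 min. The protocol gives neither the expected uptake nor the effect per minute of either kind of care, so neither the size nor the direction of any net bias can be computed. Neither a positive nor a null result would isolate the effect of OMT added to the same IBCLC care.

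**What to change.** 1. In section 2 (aim, questions, hypotheses and expected outcomes) and in the reported conclusions, state the contrast as follows. One arm has a shared IBCLC base of two face-to-face sessions and two telehealth calls (up to 120 min) plus up to three osteopathic consultations. The other has that base with up to 90 min more IBCLC telehealth: 2 × 15 min from longer calls and 2 × 30 min as required. This fits the protocol's own rationale in section 1.7: "The benefits of combining IBCLC with osteopathic care are unknown".
2. State that a positive result means that the combined package did better, and a null result that no difference between the packages was shown. Neither is the effect of OMT added to the same IBCLC care.
3. Optionally, report delivered IBCLC and OMT minutes by arm, so that readers can see how large the gap was in practice.

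Items 1 and 2 are changes of wording. Visits, allocation, outcomes and sample size stay as they are. The price is a narrower claim. Item 3 needs contact length to be available for each session.

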4.2 Randomisation and blinding

MIDs will be randomly allocated to one of two groups using a computer-generated randomisation sequence generated by a person not otherwise involved in the trial. Randomisation will be on a 1:1 allocation.

Assessors will be blinded to group allocation. Given the nature of the interventions, MIDs cannot be blinded to intervention.

4.3 Selection methods – inclusion/exclusion criteria

4.3.1 Inclusion criteria

To be eligible to enrol in the trial, an MID must meet the following criteria:

- Mother must have read the information sheet (Appendix 5.1) and signed the consent form (Appendix 6.1).
- MID must have an intake BBAT score of ≤ 5
- Mother must be 18 years of age or older
- In order to provide informed consent, the mother requires a certain level of proficiency in English. If she is not sufficiently proficient in English, the mother can use the Federal Government's Telephone Interpreter Service. This can be organised by the CI at short notice. <https://www.tisnational.gov.au/Our-services/>, <https://www.vic.gov.au/interpreters-and-translations>. Given prior notice, the CI can organise the translation service to be available at the time of the appointments with the IBCLC and Osteopaths. Alternatively, the mother can provide her own support person to help with translation.
- Mother must self-identify as having difficulty breastfeeding
- Mother must be breastfeeding, attempting to breastfeed, or wishing to re-establish breastfeeding
- Infant must be < 6 months of age at the time of enrolment
- Infant gestation at birth must be ≥ 37 weeks

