4.4.1 Bristol Breastfeeding Assessment Tool (BBAT) (Appendix 7.1)

The BBAT is a valid and reliable tool for measuring change in infant breastfeeding mechanics. [52] It was developed to measure frequently encountered postpartum breastfeeding difficulties.

The BBAT measures five aspects of breastfeeding:

- 1 Positioning
- 2 Attachment
- 3 Sucking

- 4 Swallowing
- 5 Comfort

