5.0 Data Analysis

Patient demographic data will be analysed using descriptive statistics and include mean, mode, standard deviation and interquartile range for the chosen variables.

Analyses for the purpose of generating hypotheses will be conducted using the statistical software package R (version 4.1.0 and R Studio version 2022.07.1). Wilcoxon signed rank tests with continuity

correction will be used to calculate p values for changes in BBAT, BSES-SF and VAS scores pre- and post-intervention and Wilcoxon rank-sum tests will be used to determine whether BBAT and BSES-SF scores differ between control and intervention groups.

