15.1 Personal Data

1. Full name mother
2. Full name child
3. Mother's date of birth
4. Child's date of birth
5. Child's gender
6. Mother's contact information
7. Mother's emergency contact information

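### The only between-arm test named cannot use infant age, which is already collected across a six-month range; adjusting would be a cheap but assumption-dependent gain in precision

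*Protocol*

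**What the plan says.** - **Eligibility (Protocol 4.3.1).** The age limit is "Infant must be < 6 months of age at the time of enrolment". Two other criteria narrow the population: "Infant gestation at birth must be ≥ 37 weeks" and "MID must have an intake BBAT score of ≤ 5". The BBAT limit is the same at every age.
- **Allocation (Protocol 4.2).** "MIDs will be randomly allocated to one of two groups using a computer-generated randomisation sequence", in a 1:1 ratio. No stratification or other balancing on age is described.
- **Analysis (Protocol 5.0).** Within arms, pre- and post-intervention scores are compared by signed rank tests. Between arms, "Wilcoxon rank-sum tests will be used to determine whether BBAT and BSES-SF scores differ between control and intervention groups". No covariate or stratum is mentioned. The only adjustments mentioned in the protocol concern possible bias from withdrawals (section 18).
- **Data (Protocol 15.1).** The items recorded include "Child's date of birth", so age at enrolment can be derived.
- **Sample size (Protocol 7.0).** SD 2, MCID 1.5, alpha 0.05 and power 80% give 31 per group, 62 in total, and 70 after 10% drop-out.

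**The concern.** A newborn and a five-month-old can enter with the same BBAT score. It is plausible, though the documents do not say so, that their expected course over the next four to eight weeks differs. If it does, age explains part of the spread in follow-up scores, and a two-sample rank-sum test leaves that part in the error. With about 31 analysed dyads per arm, the arms may also differ somewhat in age by chance, and the named test has no means of allowing for it.

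At stake are some precision and the ease of interpreting the result. If the arms turn out visibly different in age, an adjustment chosen afterwards looks data-driven, while leaving it out invites challenge. Naming the covariate beforehand removes that dilemma.

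**Working it through.** **1. Reproduce the plan's figure.** Inputs from Protocol 7.0: difference 1.5, SD 2 (standardised 0.75), alpha 0.05 (taken as two-sided), power 80%.
- Two-sample t-test: 28.9 per group.
- Divided by the rank-sum test's relative efficiency under normality, 0.955: 28.9 / 0.955 = 30.3, so 31 per group, as stated.
- Drop-out: 62 / 0.9 = 68.9, so 69, or 70 for equal groups.

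The planned size therefore matches an unadjusted rank-sum test with SD 2 as the total variability.

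**2. Size of chance age imbalance.** Assumption: ages uniform over 0 to 26 weeks; the documents give no distribution.
- SD of age = 26 / √12 = 7.51 weeks.
- SE of the difference in mean age = 7.51 × √(2/31) = 1.91 weeks.
- Median absolute difference = 0.674 × 1.91 = 1.3 weeks.
- 95% limit = 1.96 × 1.91 = 3.7 weeks.

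**3. Effect on the BBAT difference.** Let r be the correlation between age and outcome (assumed). The slope is r × 2 / 7.51 points per week. Power is for a two-sample t comparison with 31 per arm and standardised difference 0.75 / √(1 − r²).

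| r | Slope per week | Shift at 1.3 weeks | Shift at 3.7 weeks | Share of MCID at 3.7 weeks | Power after adjustment |
|---|---|---|---|---|---|
| 0 | 0 | 0 | 0 | 0 | 82.8% |
| 0.1 | 0.027 | 0.03 | 0.10 | 7% | 83.1% |
| 0.2 | 0.053 | 0.07 | 0.20 | 13% | 84.3% |
| 0.3 | 0.080 | 0.10 | 0.30 | 20% | 86.1% |
| 0.4 | 0.107 | 0.14 | 0.40 | 27% | 88.7% |

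Against 82.8% unadjusted, the gain is 0.3 points at r = 0.1 and 1.5 to 5.9 points at r = 0.2 to 0.4. The SE falls by the factor √(1 − r²), that is by 2% to 8% over the same range.

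**4. Simulation of the named test against an age-adjusted linear model.** 31 per arm, uniform ages, normal outcome with SD 2, 8,000 runs per setting.

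| r | Rank-sum type I error | Rank-sum power | Adjusted-model power |
|---|---|---|---|
| 0 | 4.9% | 81% | 82% |
| 0.3 | 4.8% | 81% | 86% |
| 0.5 | 4.9% | 80% | 91% |

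A small part of the difference comes from using a linear model on normal data, as the row for r = 0 shows. In the roughly 13% of trials whose age imbalance exceeds 1.5 SE (1.5 × 1.91 = 2.9 weeks), the rank-sum false-positive rate was about 7% at r = 0.3 and 14% at r = 0.5. Averaged over all randomisations it stays near 5%.

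**The case against.** The strongest reply is that nothing stated in the protocol is wrong. The rank-sum test is valid under randomisation, its sample size reproduces, and simulated power stays at 80% to 81% even at r = 0.5. A wide age range is normal in a pragmatic trial. This stands, and it rules out three stronger readings that a reader might infer.

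- **That age imbalance biases the estimated OMT effect.** It does not on average. Chance imbalance is part of the sampling error the test already allows for; the harm is conditional on an imbalance having occurred.
- **That a sizeable imbalance is likely.** The 3.7 weeks is exceeded in only about 5% of trials. The median is 1.3 weeks, which moves the BBAT difference by 5% to 9% of the MCID at r = 0.2 to 0.4.
- **That the documents show breastfeeding difficulty changes with age.** They do not. Section 4.4.1 says of the BBAT that "It was developed to measure frequently encountered postpartum breastfeeding difficulties", which says nothing about infant age.

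Two further objections limit the size. Age-related variance is already inside the planning SD of 2 unless that SD came from a narrower age range, which the documents do not show. And the relevant correlation is what age adds once baseline BBAT is in the model; the figures above do not net that out, so they are upper values if the two overlap.

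It can also be said that covariates are usually left to the SAP. That carries less weight here, because section 5.0 does not leave the between-arm method open: it names a test that takes no covariate.

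**Conclusion.** The point holds as a modest matter of precision. Section 5.0 commits the between-arm comparison to an unadjusted test while a plausibly prognostic baseline variable, spread over six months and not described as balanced, is already being recorded.

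The gain rests on the assumed correlation and on the assumed age distribution, normal outcome and SD of 2. It is worth having at correlations of 0.2 or more and negligible at 0.1 or less. Neither the planned size nor the overall type I error is shown to fail. The case for acting is that little is lost if age proves irrelevant, and that an adjustment is far more credible if fixed before the data are seen.

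**What to change.** In section 5.0, name one between-arm model for BBAT, and likewise for BSES-SF: follow-up score on arm, baseline score and infant age at enrolment, with age continuous and derived from date of birth. A proportional-odds model stays close to the rank-sum test; ANCOVA gives a mean difference on the scale of the MCID. Choose one beforehand and state its effect measure. Keep the unadjusted rank-sum test as a sensitivity analysis.

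No new data are needed, and age costs one degree of freedom. The real change is that the rank-sum test gives up its primary place and the effect measure becomes tied to the chosen model (an odds ratio or a mean difference). The sample size need not change.
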